7.4 Additional Reporting Requirements to CFCCC DSMB

Site must report AE, SAE, deviations, violations, and unanticipated problems according to their institutional policies. Institutions must also report AE, SAE, deviations, violations, and unanticipated problems to the DSMB in the following timeframes:

Adverse Events/Serious Adverse Events

Event Type	Reporting Timeframe to CFCCC DSMB (Notification is done by entering this information into OnCore within the timelines below)
Serious Adverse Events (all attributions) that meet all of the following criteria: 
 ▪ Unexpected ▪ Grades 3-5 	5 business days from date the PI is aware of the event

CONFIDENTIAL

This material is the property of the [UC Irvine Chao Family Comprehensive Cancer Center](#). Do not disclose or use except as authorized in writing by the study sponsor.
Page 36 of 57

▪ Occurring during treatment or within 30 days of the end of treatment*	
Adverse Events that meet all of the following criteria: ▪ Unexpected ▪ Study related (possibly, probably, or definitely) ▪ Grades 3-4 ▪ Occurring during treatment or within 30 days of the end of treatment*	5 business days from date the PI is aware of the event
All other Adverse Events and Serious Adverse Events should be reported as noted in the 'Recording of Events' section	Prior to each scheduled progress review.

* Investigators are not obligated to actively seek information regarding the occurrence of new AEs or SAEs beginning after the 30-day post-treatment period. However, if the investigator learns of such an event and that event is deemed relevant to the study, he/she should promptly document and report the event.
	

Deviations and Violations

Event Type	Reporting Timeframe to CFC CCC DSMB (Notification is done by entering this information into OnCore within the timelines below)
Violations as defined above (e.g. wrong dosage of drug administered, safety procedures not being conducted at specific time points).	5 business days from the date the PI is aware of the event
Deviations as defined above, including: ▪ Planned deviations (e.g. rescheduling a visit that will be out of window due to a holiday) ▪ Unplanned deviations (e.g. rescheduled visit, a missed routine safety laboratory test for a participant with previously normal values)	Prior to each scheduled progress review

CONFIDENTIAL

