Grade 2 that persists or recurs after resuming the same dose despite maximal supportive measures	Suspend dose until toxicity resolves to ≤Grade 1.
Grade 3 or 4 or requires hospitalization	Resume at next lower dose.

Dose level reductions should be made in 50 mg increments. For example, if the starting dose of abemaciclib for a study is 150 mg q12 hours, dose reduction 1 would be 100 mg q12 hours, dose reduction 2 would be 50 mg q12 hours.

General Guidance for Interstitial lung disease (ILD)/Pneumonitis events

Interstitial lung disease (ILD) / pneumonitis has been identified as an adverse drug reaction for abemaciclib. Adverse events reported included events such as interstitial lung disease, pneumonitis, obliterative bronchiolitis, organizing pneumonia, pulmonary fibrosis. The majority of events were Grade 1 or Grade 2 with serious cases and fatal events reported.

Monitor for clinical symptoms or radiological changes indicative of ILD/pneumonitis and please ask patients to report any new or worsening pulmonary symptoms. Symptoms may include hypoxia, cough, dyspnea, or interstitial infiltrates on radiologic exams.; these symptoms should be investigated and treated as per local clinical practice and/or guidelines (including corticosteroids as appropriate). Infectious, neoplastic, and other causes for such symptoms should be excluded by means of appropriate investigations. Investigations may include imaging such as high resolution computer tomography (HRCT), bronchoalveolar lavage (BAL), and biopsy as clinically indicated (see also Table).

Interstitial Lung Disease (ILD)/Pneumonitis

ILD/Pneumonitis Dose Management Guidelines	
CTCAE Grade	Action
Grade 1-2	No dose modification required
Grade 2 that persists or recurs after resuming the same dose despite maximal supportive measures within 7 days to baseline or Grade 1	Suspend dose until toxicity resolves to ≤Grade 1. Resume at next lower dose.
Grade 3-4	Discontinue abemaciclib

Non-hematological Toxicities (excluding Diarrhea, ALT Increased, and ILD Pneumonitis)

Non-Hematological Toxicity Dose Management Guidelines (excluding Diarrhea, ALT

CONFIDENTIAL

This material is the property of the [UC Irvine Chao Family Comprehensive Cancer Center](#). Do not disclose or use except as authorized in writing by the study sponsor.

Increased, and ILD Pneumonitis)	
Event	Action
Grade 1-2	No dose modification required

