7.3 Reporting Requirements for Adverse Events

Adverse events, serious adverse events, deviations, violations, and unanticipated problems must be entered into the clinical trial management system (CTMS), OnCore, and must also be reported to the following entities according to the timelines mentioned in the chart below. Serious adverse events collection will start at the time patient signs consent until 30 days after the end of treatment. Adverse events will be collected from the time the research patient begins treatment until 30 days after the end of treatment. All adverse events/serious adverse events should be followed until resolution or stabilization.

Event Type	Coordinating Center/Medical Monitor	UCI IRB	Eli Lilly Pharmaceuticals*	CFCCC DSMB
Unanticipated Problem (UP)	Within 24 hours from date the site is aware of the event, the site should enter this information into OnCore. An email notification should also be sent via email to [contact] and [contact] .	Within 5 business days submit an Unanticipated Problem Report (UP) . Current policy can be found here .	Within 15 business days of learning of the event. Submit an SAE Form to Eli Lilly's IIR Portal for Trial Management (https://www.lillyinvestigatorresearch.com) OR via [contact]). Serious adverse events should be reported to Lilly using a CIOMS Form or other form acceptable to Lilly.	Within 5 days from date PI is aware of the event. This information must be reported into OnCore.
AEs and SAEs (non-Unanticipated Problem)	Please refer to section 7.4 for reporting timeframes on AEs and SAEs.	N/A	Only SAEs are required to be reported within 15 business days of learning of the event. Please see section 7.6 below for additional reporting for SAEs that are non-UPs.	Please refer to section 7.4 for clarification on reporting timeframes for AEs and SAEs.
Non-compliance	N/A	N/A	N/A	Please refer to section 7.4 for reportable deviations/violations.

CONFIDENTIAL

This material is the property of the [UC Irvine Chao Family Comprehensive Cancer Center](#). Do not disclose or use except as authorized in writing by the study sponsor.

Serious or continuing non-compliance	Within 24 hours via email to [contact] and [contact]	Within 5 business days submit a New Information Report	N/A	Within 5 days from date PI is aware of the event.

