7.5 Additional Clinical Reporting Requirements to Eli Lilly Pharmaceuticals

Eli Lilly Pharmaceuticals requires that all SAEs related to study drug are reported via Eli Lilly's IIR Portal for Trial Management (<https://www.lillyinvestigatorresearch.com>) OR via [contact]). Serious adverse events should be reported to Lilly using a CIOMS Form or other form acceptable to Lilly. Eli Lilly Pharmaceuticals does not require the report of other events of special interest.

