8.0 DRUG INFORMATION

8.1 Abemaciclib

A list of the adverse events and potential risks associated with Abemaciclib can be found in the investigator brochure available in OnCore

- Other names for the drug(s): Verzenio
- Classification - type of agent: Antineoplastic
- Mode of action: Cyclin-dependent kinase inhibitor
- Storage and stability: Store at room temperature, refer to product label for specific storage range and instructions.”
- Protocol dose: 150 mg BID, [Abemaciclib will be provided in 50mg tablets only](#)
- Preparation: N/A
- Route of administration for this study: Oral
- Availability: Provided by Eli Lilly
- Side effects: Common side effects are Diarrhea, Neutropenia, Nausea, abdominal pain, fatigue, anemia, leucopenia, vomiting, thrombocytopenia, thromboembolism

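### Section 7.4 has no expedited DSMB route for a death classed as expected (fatal ILD/pneumonitis is the concrete case), and Sections 7.3 and 7.5 differ on which SAEs go to the drug supplier

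*Combined protocol and SAP*

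**What the plan says.** **DSMB.** The Section 7.4 table expedites "Serious Adverse Events (all attributions) that meet all of the following criteria". The first two criteria read "Unexpected ▪ Grades 3-5" and the third is the time window. The timeframe is 5 business days. For the remainder, "All other Adverse Events and Serious Adverse Events should be reported as noted in the 'Recording of Events' section", with the timing "Prior to each scheduled progress review". No row is specific to deaths.

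**Expectedness.** Section 7.1.1 looks to the brochure or package insert, to whether the event is listed at the severity seen, and to risk information in the protocol or consent. Section 7.2 Step 4, written for expedited reporting, looks to the protocol's Agent Information section, the package insert and the Investigator's Brochure. It treats an event as unexpected if either its type or its severity is not listed.

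**Listed toxicities.** On ILD/pneumonitis, Section 4.2.1 states: "The majority of events were Grade 1 or Grade 2 with serious cases and fatal events reported". Section 8.1 does not mention ILD and gives no grades: "Common side effects are Diarrhea, Neutropenia, Nausea, abdominal pain, fatigue, anemia, leucopenia, vomiting, thrombocytopenia, thromboembolism".

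**IRB.** In the 7.3 chart an event is expedited to the IRB only as an Unanticipated Problem. The entry for other SAEs is N/A.

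**Supplier.** Section 7.3: "Only SAEs are required to be reported within 15 business days of learning of the event". Section 7.5: "Eli Lilly Pharmaceuticals requires that all SAEs related to study drug are reported". Section 7.3 also sends the reader to 7.6 for further SAE reporting, but 7.6 deals with milestones, enrolment updates and invoices.

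**The concern.** The order of priority is hard to defend. An unexpected Grade 3 SAE unrelated to treatment goes to the DSMB in 5 business days, and so does a violation such as a wrong dose. A death caused by the study drug may not, if that toxicity is already known to kill.

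These patients have localized disease and are treated before surgery with curative intent (Section 1.4). The available text gives no numeric stopping rule for toxicity: Section 10.2 promises interim looks at side effects without timing, and Section 11.3.2 mentions stopping rules only in general terms. Prompt notice of a drug death is therefore one of the main ways in which the independent board could reassess the balance of risk for later patients.

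The supplier wording is a smaller matter. An SAE that the investigator judges unrelated falls within 7.3 but outside 7.5, so two coordinators could handle it differently.

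**Working it through.** The plan has no figure to reproduce here. The check is to follow each kind of event through the rules.

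**A. Treatment-related fatal ILD/pneumonitis, within the window**
1. Expectedness under 7.1.1: Section 4.2.1 names the toxicity and says that it has been fatal. The event is consistent with the protocol's own risk information in both type and severity, so it can be classed as expected.
2. 7.4, SAE row: it must be unexpected AND Grade 3-5 AND in the window. The first condition fails.
3. 7.4, AE row: this also requires unexpected and stops at Grade 4. It fails.
4. 7.4, default row: DSMB before the next progress review.
5. Unanticipated Problem (7.1.1): this needs unexpected AND related AND greater risk than previously known. The event is not unexpected in nature or severity. It could qualify on frequency or on the characteristics of this population. If it does not, the IRB entry in 7.3 is N/A.
6. Supplier: 15 business days under 7.3 (3 weeks, 21 calendar days). As a related SAE it also falls within 7.5.

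**B. The same death under 7.2 Step 4**
Section 8.1 does not list ILD. If absence from the Agent Information section is enough, the death is unexpected and takes the fast route. If a listing in any one of the three sources makes it expected, the answer turns on the brochure and package insert, which are not in the documents. Section 8.1 itself defers to the brochure. Sections 7.1.1 and 7.2 can therefore classify one death in two ways.

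**C. Treatment-related death from a toxicity not listed at fatal severity**
An example is thromboembolism, which 8.1 names without a grade. If no other reference lists it as fatal, the severity test makes it unexpected. It is Grade 5 and goes to the DSMB in 5 business days. There is no gap.

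**D. SAE judged unrelated to study drug**
It is reportable to the supplier under 7.3 but outside the requirement stated in 7.5. The scopes differ.

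**Size of the DSMB delay**
- Accrual (10.2): 30 to 32 patients over four years, so 30/4 = 7.5 to 32/4 = 8 a year.
- Review interval: not stated. Assume 6 to 12 months.
- Enrolled in 6 months: 7.5 × 0.5 = 3.75 to 8 × 0.5 = 4.
- Enrolled in 12 months: 7.5 to 8.
- Enrolled in 5 business days (one week): 7.5/52 = 0.14 to 8/52 = 0.15.

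These counts are for a full interval at constant accrual. A death midway through an interval would wait about half as long.

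**The case against.** Four arguments count against the point.

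- **Severity test.** A reader might infer that a death from any toxicity named in the protocol is expected and so escapes expedited reporting. The documents do not support that. Section 7.1.1 tests the severity observed, and 7.2 Step 4 says that an unlisted type or an unlisted severity is enough. The limbs of 7.1.1 are separated by semicolons with no connective, and reading them as cumulative would widen the gap, but the wording of 7.2 points the other way. This argument stands and confines the point to toxicities listed with a fatal outcome.
- **Fatal ILD may still be expedited.** It may be unexpected under 7.2, or an Unanticipated Problem on frequency or population. This is true as far as it goes. It shows that the fast route is possible, not that it is assured, and the difference depends on documents outside the protocol.
- **Other oversight exists.** Section 7.4 also invokes institutional policies, 11.3.2 makes the study team responsible for safety monitoring, and in a single-center trial the investigator will know of the death. This stands in part. The policies are not visible and may add duties, but the study team's knowledge does not replace notice to an independent board.
- **Supplier wording.** A reader might infer that under 7.5 an unrelated SAE never reaches the supplier. Nothing says that 7.5 overrides 7.3, and following 7.3 satisfies both. What remains is an inconsistency to settle, not a lost report.

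**Conclusion.** The point holds in a narrow form. Section 7.4 gives no assured expedited DSMB route for a death classed as expected. Fatal ILD/pneumonitis is the one case that the protocol itself supplies for abemaciclib, and its classification depends on whether 7.1.1 or 7.2 is applied. On the slow route, the DSMB hears before the next progress review and the IRB chart entry is N/A unless the event is an Unanticipated Problem. The supplier still hears of a related death within 15 business days.

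The practical size is uncertain. About 4 to 8 patients could enrol over one review interval, but that rests on assumed intervals of 6 to 12 months. It also assumes that enrolment continues unchanged after the death, which the documents do not say. The counts show the possible length of the delay, not harm.

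The brochure, package insert and institutional policies are not in the documents, and some text between 7.4 and 7.5 was not available. Any of these could add duties. The supplier scope and the 7.6 reference are inconsistencies to correct and carry less weight. The change should be made because it closes a stated gap at little cost.

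**What to change.** 1. Add a row to the 7.4 DSMB table: any Grade 5 event, expected or not, in the same time window as the existing SAE row, reported within 5 business days of PI awareness.
2. Use one expectedness reference in 7.1.1 and 7.2, and state whether its conditions are alternatives or cumulative. If the 8.1 list stays part of that reference, make it agree with the adverse drug reactions named in 4.2.1.
3. Confirm with the supplier which SAEs it requires, then make 7.3 and 7.5 say the same. Until then, following 7.3 meets both.
4. Correct the reference in 7.3 that points to 7.6.

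The cost is a wording amendment and a few extra expedited OnCore entries in about 30 patients. Sample size, endpoints and analysis are unaffected.

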7.5 Additional Clinical Reporting Requirements to Eli Lilly Pharmaceuticals

Eli Lilly Pharmaceuticals requires that all SAEs related to study drug are reported via Eli Lilly's IIR Portal for Trial Management (<https://www.lillyinvestigatorresearch.com>) OR via [contact]). Serious adverse events should be reported to Lilly using a CIOMS Form or other form acceptable to Lilly. Eli Lilly Pharmaceuticals does not require the report of other events of special interest.

7.6 Other Non-Clinical Reporting Guidelines to Eli Lilly Pharmaceuticals

Other information such as milestone dates, milestone dates met, enrollment updates, protocol amendments, site information, and expenses (invoices) can be updated in Eli Lilly's IIR Portal for Trial Management (<https://www.lillyinvestigatorresearch.com>) by the study members assigned by the principal investigator.

8.0 DRUG INFORMATION

8.1 Abemaciclib

A list of the adverse events and potential risks associated with Abemaciclib can be found in the investigator brochure available in OnCore

- Other names for the drug(s): Verzenio
- Classification - type of agent: Antineoplastic
- Mode of action: Cyclin-dependent kinase inhibitor
- Storage and stability: Store at room temperature, refer to product label for specific storage range and instructions.”
- Protocol dose: 150 mg BID, [Abemaciclib will be provided in 50mg tablets only](#)
- Preparation: N/A
- Route of administration for this study: Oral
- Availability: Provided by Eli Lilly
- Side effects: Common side effects are Diarrhea, Neutropenia, Nausea, abdominal pain, fatigue, anemia, leucopenia, vomiting, thrombocytopenia, thromboembolism

8.2 Fulvestrant

A list of the adverse events and potential risks associated with Fulvestrant are found in package insert.

- Other names for the drug(s): Faslodex

CONFIDENTIAL

This material is the property of the [UC Irvine Chao Family Comprehensive Cancer Center](#). Do not disclose or use except as authorized in writing by the study sponsor.

- Classification - type of agent: Antineoplastic
- Mode of action: Estrogen receptor antagonist
- Storage and stability: Refrigerate, 2 to -8°C, protect from light, store in original cartoon until time of use
- Protocol dose: Supplied at 50mg/ml. Protocol dose 500 mg.
- Preparation: Solution
- Route of administration for this study: Intramuscular
- Availability: Commercially available
- Incompatibility: There are no known drug-drug interactions. Fulvestrant does not significantly inhibit any of the major CYP isoenzymes, and studies of co-administration of fulvestrant with midazolam indicate that therapeutic doses of fulvestrant have no inhibitory effects on CYP3A4 or alter blood levels of drug metabolized by that enzyme. Also, although fulvestrant is partly metabolized by CYP3A4, a clinical study with rifampin, an inducer of CYP3A4, showed no effect on the pharmacokinetics of fulvestrant. Clinical studies of the effect of strong CYP3A4 inhibitors on the pharmacokinetics of fulvestrant have not been performed.
- Handling: Use appropriate precautions for receiving, handling, administration, and disposal. Gloves (single) should be worn during receiving, unpacking, and placing in storage. NIOSH recommends double gloving, a protective gown, ventilated engineering controls (a class II biological safety cabinet or a compounding aseptic containment isolator), and closed system transfer devices (CSTDs) for preparation. Double gloving and a protective gown are recommended during administration (NIOSH 2016).
- Side effects: Fatigue, Headache, Hot flash, Anemia, Nausea, cough, increase in creatinine, peripheral edema, dizziness, pruritus, skin rash, back pain, anorexia, hypersensitivity reactions, and thromboembolism. Increase hepatic enzymes also can occur.

Hot flashes (23.5%) are the most commonly reported adverse reaction to fulvestrant during second line hormonal therapy for breast cancer. Vaginal irritation (3.4%) has also been reported with fulvestrant.

UTI adverse reactions occurred in up to 9.3% of patients receiving fulvestrant.

Joint disorders have been reported in 9.3% of patients.

Others include nausea, vomiting, constipation, diarrhea and abdominal pain, headache, back pain, and pharyngitis.

CONFIDENTIAL

This material is the property of the [UC Irvine Chao Family Comprehensive Cancer Center](#). Do not disclose or use except as authorized in writing by the study sponsor.

Thromboembolism has been reported in patients treated with fulvestrant (3.5%). The incidence of thrombosis is less than that reported with tamoxifen (6.5%) or megestrol (4.7%) during clinical trials.

Injection site reactions with mild transient pain and inflammation occurred in 7% of patients (1% of treatments) given the single 5ml injection of fulvestrant and withdrawal secondary to that was 2.5%.

Other adverse events reported as drug-related and seen infrequently (< 1%) include thromboembolic phenomena, myalgia, vertigo, and leukopenia.

Vaginal bleeding has been reported infrequently (< 1%), mainly in patients during the first 6 weeks after changing from existing hormonal therapy to treatment with fulvestrant. If bleeding persists, further evaluation should be considered.

- Contraindications: Hypersensitivity reaction
- Warning and precaution:
 - Blood disorders: Should be used with caution in patients with bleeding diathesis, thrombocytopenia or anticoagulant use
 - Hepatic Impairment: A 250mg dose is recommended in patients with moderate hepatic impairment
 - Pregnancy: Women should be advised of potential hazard to the fetus and to avoid becoming pregnant while receiving Faslodex

8.3 Agent Accountability

Accountability for the study drug at the study center is the responsibility of the Investigator. The Investigator will ensure that the study drug is used only in accordance with this protocol. Where allowed, the Investigator may choose to assign drug accountability responsibilities to a pharmacist or other appropriate individual.

The Investigator or delegate will maintain accurate drug accountability records indicating the drug's delivery date to the site, inventory at the study center, use by each patient, and destruction.

These records will adequately document that the patients were provided the doses as specified in the protocol and should reconcile all study drug received from Eli Lilly Pharmaceuticals.

Study drug must not be used for any purpose other than the present study. Study drug that has been dispensed to a patient and returned unused must not be redispensed to a different patient.

Patients will receive instructions for home administration of Abemaciclib according to the regimen description above. Abemaciclib is to be taken twice a day. If doses of Abemaciclib are missed or held, the patient should not make up for the missed doses. Patients will be given a study medication diary to complete at home for Abemaciclib. Compliance with the dosing regimen will be assessed based on completion of the drug diary and return of unused drug (or empty bottles).

IMP Destruction

IMP will be destroyed by the sites according to their institutional policies. Documentation of IMP destruction should be made available to Eli Lilly Pharmaceuticals at the end of the study.

IMP Returns

CONFIDENTIAL

This material is the property of the [UC Irvine Chao Family Comprehensive Cancer Center](#). Do not disclose or use except as authorized in writing by the study sponsor.

Eli Lilly Pharmaceuticals will not accept returned IMP

